### ***Exploratory Analyses***

Serum bone markers (i.e., P1NP, BSAP, CTX) and additional CT bone biomarkers, measured at 3, 6, 12 and 24 months will be evaluated using a similar approach as for the primary analyses – linear mixed effects model. A compressive strength index (CSI; g2/cm4) and a torsional strength index (TSI; cm3) will be computed for each skeletal region. Finally, CT-based finite element analysis will be used to predict stiffness and strength at the hip, distal femur, and proximal tibia.

### ***Sensitivity analyses***

This analysis will assess the robustness of the efficacy conclusions regarding the choice of maximum likelihood estimation as the primary method for accounting for missing data. The primary mixed effects model described above will be repeated after multiple imputation, as described above.

### ***Analysis of Safety***

Analysis of safety will include all participants who underwent randomization and received at least one dose of the study drug. Safety endpoints will include incidence and severity of adverse events and laboratory blood chemical values. Adverse events will be characterized by system, organ, and class designation. Raw number of events and number of participants experiencing reported serious adverse events and adverse events will be reported.

## Analysis Plan Summary

Endpoint	Statistical Method	Model/Covariates	Missing Data	Objective
% Change from Baseline at 6,12 months with total hip and femoral neck aBMD, DXA	MEM	Baseline total hip/ femoral neck aBMD, visit, WISCI score; (subjects as random effects)	MLE	Primary Analysis
% Change from Baseline at 6,12 months with total hip aBMD, DXA	MEM	Baseline total hip aBMD, visit, WISCI score; (subjects as random effects)	Multiple Imputation	Sensitivity Analysis
% Change from Baseline at 6,12 months with total hip aBMD, DXA (a)	MEM	Baseline total hip aBMD, visit, WISCI score, (subjects as random effects)	MLE	Secondary, Interaction Analysis
% Change from Baseline at 6, 12 months with femoral neck aBMD, DXA (b)	MEM	Baseline total hip aBMD, visit, WISCI score; (subjects as random effects)	MLE	Secondary Analysis
% Change from Baseline at 6,12, months with QCT Int.vBMC Femoral Epiphysis (b)	MEM	Baseline total hip aBMD, visit, WISCI score; (subjects as random effects)	MLE	Secondary Analysis
% Change from Baseline at 6,12, QCT Int.vBMC Femoral Metaphysis (b)	MEM	Baseline total hip aBMD, visit, WISCI score; (subjects as random effects)	MLE	Secondary Analysis
% Change from Baseline at 24 months with total hip aBMD, DXA (c)	MEM	Baseline total hip aBMD, visit, WISCI score; (subjects as random effects)	MLE	Secondary Analysis
% Change from Baseline at 24 months with	MEM	Baseline total hip aBMD, visit, WISCI	MLE	Secondary Analysis

femoral neck aBMD, DXA (c)		score; (subjects as random effects)		
% Change from Baseline at 24 months with QCT Int.vBMC Femoral Epiphysis (c)	MEM	Baseline total hip aBMD, visit, WISCI score; (subjects as random effects)	MLE	Secondary Analysis
% Change from Baseline at 24 months with QCT Int.vBMC Femoral Methaphysis (c)	MEM	Baseline total hip BMD, visit, WISCI score; (subjects as random effects)	MLE	Secondary Analysis

(a) Secondary analysis phase 1: Interaction Analysis for primary endpoint with WISCI; (b) Secondary analysis phase 2: Secondary endpoints at 12 months; (c) Secondary analysis phase 3: Primary and Secondary endpoints at 24 months. aBMD (areal bone mineral density); MEM (mixed effects model); MLE (maximum likelihood estimates); WISCI (walking index for spinal cord injury).

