1.1. Rationale

Spinal cord injury results in acute bone loss which is rapid and profound.

Spinal cord injury (SCI) results in marked acute loss of bone, primarily limited to those bony structures that are below the level of the neurologic lesion and non-weight-bearing, with little or no loss of bone at the spine and in bony structures that are supraspinal.^{1,2} The bone loss occurs rapidly, with the greatest decrease in bone density observed during the first 6-18 months after spinal cord injury, and is profound in magnitude, commonly being in the range of 15-30% at the hip, and potentially even higher at sites of less weight-bearing and of greater trabecular content below the hip.^{1,2} The degree of bone loss has been shown to be highly dependent on the degree of loading, with individuals having incomplete motor lesions and capable of some degree of weight-bearing having less bone loss than those with motor complete lesions.³ Lower extremity bone loss is similar in paraplegics and quadriplegics with similar motor function loss; upper extremity bone mass is unaffected in paraplegics but variably affected in quadriplegics, dependent on the degree of impairment of upper extremity function⁴. Age, weight and gender are important determinants of bone loss.³ Initially, bone mineral density (BMD) decline is reported to be most marked in areas rich in trabecular bone, with relative sparing of cortical bone ^{2,5-8} though recent studies from our group indicate significant acute loss of cortical bone as well ⁹ This enhanced rate of bone loss can be observed for between 2 and 5 years after acute SCI, at which time a new steady state is reached and bone resorption and bone formation become once again tightly coupled, but now at a new “set point” with bone mass that is 30-50% below the level prior to the injury.^{2,5-7} After this point in time, there is a much reduced rate of bone loss, with other secondary causes of bone loss, e.g., estrogen withdrawal, endocrinopathies, being potentially important contributors to further changes in bone status.

Loss of bone mass after acute SCI is paralleled by a marked decrease in bone strength.

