## ***Primary analyses***

Group comparisons will be tested with a linear mixed-effects model with the percentage-change from baseline to months 6 and 12 in aBMD at the total hip and femoral neck. Baseline aBMD at the total hip and femoral neck, study visit, ambulatory status measured by WISCI and interaction of WISCI with visit will be fitted as random factors. aBMD by group interaction will be considered statistically significant at  $p < 0.05$ . Raw effect sizes will be calculated as differences between groups at each time point. Multiplicity will be handled by utilizing a fixed-sequence approach to testing, with initial analysis of total hip ( $\alpha=0.05$ ) and if successful followed by femoral neck ( $\alpha=0.05$ ).

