## ***Secondary analyses***

Secondary analysis will be divided into three main sections:

- a) Effect of functional capacity (WISCI) on aBMD of total hip and femoral neck percent-change; A secondary interaction analysis will be performed for the primary endpoint, exploring the effect of WISCI. The interaction of treatment with WISCI score will be fitted as a fixed effect (in addition to the WISCI score itself), with the resulting estimated treatment differences being shown for continuous scores of the WISCI scale.
- b) Secondary endpoint analysis at 12 months;

The primary analysis described above will be applied for all the three key secondary endpoints at 6, and 12 months visits, with the fixed sequence order described above. Appropriate p-values adjustments to compensate for a possible increased risk in Type I errors due to multiple secondary outcomes measurements will be done using a stepwise Dunnett procedure. All reporting will include both adjusted p values and raw effect sizes.

c) Primary and secondary endpoint analysis at 24 months.

Primary endpoint (total hip and femoral neck aBMD, measured by DXA) and secondary endpoints will be analyzed at 24 months. Here, we will study 4 groups of patients: 24 months of treatment, 24 months of no-treatment, switch from treatment to placebo at 12 months, switch from placebo to treatment at 12 months. A linear mixed model with the four groups, controlling for Baseline aBMD at the hip and ambulatory status measured by WISCI will be fitted to predict percent-change from baseline for each endpoint.

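### The primary model's within-patient covariance is not specified; on its ordinary reading it assumes equal variance at months 6 and 12, which would misstate the month-12 standard error if the spread differs between visits

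*SAP*

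**What the plan says.** The SAP describes the primary model in two places.

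- **Analysis Plan Summary, primary row:** a mixed-effects model for months 6 and 12, with "Baseline total hip/ femoral neck aBMD, visit, WISCI score; (subjects as random effects", and maximum likelihood for missing data.
- **Primary analyses:** a "linear mixed-effects model with the percentage-change from baseline to months 6 and 12 in aBMD at the total hip and femoral neck", in which baseline aBMD is listed as a random factor and "study visit, ambulatory status measured by WISCI and interaction of WISCI with visit will be fitted as random factors".

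The significance rule is attached to another term: "aBMD by group interaction will be considered statistically significant at" the 0.05 level. The time-point differences are then described as a summary: "Raw effect sizes will be calculated as differences between groups at each time point".

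Secondary analyses (b) carries the model over: "The primary analysis described above will be applied for all the three key secondary endpoints". The multiple-imputation sensitivity analysis repeats the same model. Diagnostics plans a look at residuals but names no remedy. No covariance structure, visit-specific residual variance, robust standard error or df method appears anywhere in the SAP.

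Hypothesis 1a (SAP, Study Objectives) and the primary endpoint in Protocol section 2.2 both concern change at one year.

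**The concern.** With subject as the only random effect and one residual variance, the model has compound symmetry: months 6 and 12 share one variance, estimated as roughly the average of the two. The outcome is cumulative percent change, zero for everyone at baseline, and Protocol section 1.1 describes continuing loss: "The bone loss occurs rapidly, with the greatest decrease in bone density observed during the first 6-18 months after spinal cord injury". If patients lose bone at different rates, their values could still be fanning out between month 6 and month 12. The pooled variance would then be too small for the month-12 comparison and too large for the month-6 one.

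At stake are the error rate and the confidence interval of the one-year group difference, at the total hip and femoral neck and at the QCT knee endpoints that reuse the model.

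**Working it through.** **The plan's own figure.** Protocol section 14.3 claims 80% power for d = 0.74 with 30 per group. A two-sided 0.05 two-sample comparison gives 80.5% (noncentral t) or 81.8% (normal). The alternative statement, a 6.5-point difference with SD 9.02, gives d = 6.5/9.02 = 0.72 and power of 78.4% (t) or 79.7% (normal). The figure is reproduced to within two points. It uses only a month-12 SD; the documents give no month-6 SD.

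**Inputs.** 30 per arm and dropout below 20% (Protocol 14.3); visits at months 6 and 12 (SAP). Assumptions: two-sided alpha, and k = SD6/SD12 varied from 1.25 to 0.5.

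**Closed form** (complete, balanced data, random intercept, group-by-visit means). The pooled variance is (SD6² + SD12²)/2, so at month 12

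model SE / true SE = sqrt((1 + k²)/2), and type I error = 2 × [1 − Φ(1.96 × that ratio)].

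Example, k = 0.8: sqrt((1 + 0.64)/2) = 0.906; 1.96 × 0.906 = 1.775; type I error 7.6%.

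**Simulation under no effect.** 30 per arm, 10% missing at month 12, 3,000 runs per scenario, covariates for baseline, WISCI and WISCI-by-visit, month 6-12 correlation 0.7 (0.5 and 0.8 where a range is shown), REML with t on 55 df. All error rates are for the month-12 group difference.

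| SD6/SD12 | SE ratio | Closed form | Random intercept, simulated | Unstructured, simulated |
|---|---|---|---|---|
| 1.25 | 1.132 | 2.65% | 2.6% | 5.0% |
| 1 | 1.000 | 5.0% | 4.6-5.1% | 4.7-5.4% |
| 0.8 | 0.906 | 7.6% | 7.4% | 5.2% |
| 0.67 | 0.850 | 9.6% | 10.0-10.4% | 5.0-5.1% |
| 0.5 | 0.791 | 12.1% | 13.6% | 5.7% |

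The first row is SD12/SD6 = 0.8, that is, spread narrowing over time.

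**The estimation method the SAP names.** With maximum likelihood and a normal reference, the random-intercept test gave 5.9-6.3% at equal variances, 9.3% at k = 0.8 and 11.6-12.3% at k = 0.67. The excess at equal variances is small-sample bias of maximum likelihood, a separate matter that REML with a df method removes.

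**Other tests the SAP might mean.** With complete balanced data, neither a group-by-visit test nor a visit-averaged group test is distorted by unequal visit variances. In the simulation (maximum likelihood, normal reference) they gave 5.7-6.0% and 6.3-6.6% at equal variances, and 7.1-7.2% and 7.1-7.7% at k = 0.67.

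**Interval width, for illustration.** With SD 9.02 at month 12, the true SE is 9.02 × sqrt(2/30) = 2.33 and the 95% half-width is 1.96 × 2.33 = 4.6 points. The model would print 4.6 × 0.906 = 4.1 at k = 0.8 (coverage 100 − 7.6 = 92.4%), or 4.6 × 1.132 = 5.2 at k = 1.25.

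**Total hip at pilot size.** From Table 2 of the protocol, left: (13.83 − 3.40)/sqrt((3.51² + 2.01²)/2) = 10.43/2.86 = 3.6. Right: (18.21 − 2.80)/sqrt((5.08² + 2.39²)/2) = 15.41/3.97 = 3.9. With 30 per arm, 3.6 × sqrt(15) gives a test statistic near 14, so a standard error wrong by 10-15% would not change the conclusion.

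**The case against.** A reader might infer that the plan imposes equal variances and that its one-year test therefore rejects too often. The documents do not support that, for three reasons.

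- **The structure is not fixed.** The SAP never names a covariance. Fitted by subject, the random visit and WISCI-by-visit terms in Primary analyses could let the variance differ between visits. This stands against any claim that equal variance is forced. It does not settle the matter. A single visit effect shared by all patients leaves the within-patient variances equal. A correlated subject intercept and visit effect plus a residual has four parameters for the three elements of a 2×2 covariance, so it cannot be identified.
- **The named test is not the month-12 difference.** The rule refers to an interaction with group, and the group-by-visit and visit-averaged readings are much less affected. This also stands. But Hypothesis 1a is a one-year statement and differences are reported by visit, so answering it needs the month-12 contrast.
- **Growing spread is an assumption.** Section 1.1 describes average loss, not variance. In Table 2, the placebo group lost more at all five lower-limb sites and had the smaller SD at each (right total hip −18.21 ± 2.39 against −2.80 ± 5.08), although these are small pilot data at one time point. WISCI-by-visit may absorb part of any fanning out. Censoring after the month-6 bone-loss threshold (Protocol section 10) could narrow the month-12 spread, and the month-12 test would then be conservative. The same censoring depends on the month-6 value, so likelihood estimation leans on the month-12-on-month-6 regression, which an equal-variance model misstates whenever the variances differ.

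The practical weight is also limited. The protocol expects much less variance for CT than for knee DXA, where it plans on d of at least 1.0.

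**Conclusion.** The point holds as a gap in specification with a calculable consequence, not as a demonstrated inflation of the primary error rate. The two SAP descriptions disagree on the random effects, and neither states the covariance, the df method or the month-12 contrast.

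On the ordinary reading of the summary table, and with the month-12 difference taken as the test, REML with a t reference gives a type I error of about 7-8% if SD6/SD12 is 0.8, about 10% if it is 0.67, and about 3% if SD12/SD6 is 0.8. The direction depends on a month-6 SD that the documents do not give. The 12-14% at a ratio of 0.5 is an extreme of the range, not an expectation.

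Total hip significance would survive effects of pilot size. What is exposed is mainly the width of reported intervals and the error rate at the QCT knee endpoints. The change is worth making because an unstructured covariance kept the month-12 error rate at 4.7-5.7% across the simulated scenarios, whichever visit had the larger variance.

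**What to change.** Reconcile Primary analyses with the Analysis Plan Summary so that they describe one model:

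- group, visit, group-by-visit and the planned covariates as fixed effects;
- an unstructured covariance for months 6 and 12 within patient, in place of the subject random intercept;
- REML with a small-sample df method such as Kenward-Roger or Satterthwaite;
- the month-12 group difference named as the test of Hypothesis 1a, in place of the interaction now cited;
- the same structure for the femoral neck, the key secondary QCT endpoints in Secondary analyses (b), and the multiple-imputation sensitivity analysis.

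Naming the month-12 difference changes the stated test as well as the covariance, and the SAP should say so openly. The cost is SAP wording and one extra covariance parameter (three instead of two). No further patients, visits or data are needed.

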2.2. Projected Outcomes and Endpoints

One year efficacy outcome results.

Mean change in BMD from baseline after one year, evaluated by DXA at the total hip, in the group of participants treated with zoledronic acid will be statistically significantly less than the mean change in BMD in the group receiving placebo (primary endpoint). It is also anticipated that there will be a statistically significant difference in mean change in BMD at one year at the femoral neck and at the knee (distal femur, proximal tibia) between these two groups.

Two year retreatment outcome efficacy results.

Retreatment of those participants who received zoledronic for the first year of the study with zoledronic acid again (zol/zol) is expected to result in a continued inhibition of bone loss, such that when compared to individuals who had received zoledronic acid for the first year and then placebo (zol/placebo), a statistically significant difference between mean changes from baseline in BMD at the hip and knee skeletal sites will be observed after 2 years.

Observation of the zol/placebo group during the second year of the study will permit definition of the duration of a single infusion of zoledronic acid. It is anticipated that at the end of 2 years there will remain a statistically significant difference in mean change in BMD at hip and knee skeletal sites in this group compared to the group receiving placebo throughout the 2 years of the study (placebo/placebo).

The group of individuals receiving zoledronic acid after a first year on placebo (placebo/zol) will be expected to show rapid bone loss during year 1 after which further bone loss will be prevented or slowed by treatment with zoledronic acid. By the end of year 2, the mean change in BMD from baseline at hip and knee skeletal sites in the placebo/zol group will be less than the mean change seen in the placebo/placebo group but greater than observed in the zol/zol group.

Markers of bone metabolism.

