## Endpoints

**Primary endpoints.** The primary endpoints in this study are the percent-change in aBMD, evaluated by DXA, in the non-dominant (1) total hip and (2) femoral neck skeletal sites. If data on the non-dominant hip are unavailable, we will use aBMD for the dominant hip. Percent-change will be calculated as  $((\text{aBMD}_{\text{follow-up}} - \text{aBMD}_{\text{baseline}}) / \text{aBMD}_{\text{baseline}}) \times 100\%$ .

**Key secondary endpoints.** Secondary endpoints include: (1) integral volumetric bone mineral content (Int.vBMC) distal femoral epiphysis, (2) Int. vBMC tibial epiphysis, and (3) Int.vBMC distal femoral metaphysis measured by QCT. Percent-change will again be calculated for each outcome.

**Additional secondary endpoints.** CT biomarkers: Trabecular volumetric bone mineral density (Tb.vBMD; g/cm^3) and cortical volumetric bone mineral content (Ct.vBMC; g) and bone volume (Ct.vBV; cm^3) at epiphyseal and metaphyseal regions. For the diaphyseal region, Ct.vBMC and Ct.vBV. WISCI.

**Exploratory endpoints.** Torsional strength index (TSI; cm^3) for each skeletal region. Stiffness and strength at the hip, distal femur, and proximal tibia determined by CT-based finite element analysis. Serum markers of bone metabolism: P1NP, BSAP (bone formation markers), and CTX (bone resorption marker).

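### The SAP's summary table contradicts its text: femoral neck is both primary and secondary, tibial epiphysis has no row, and six rows adjust for another site's baseline

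*SAP*

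**What the plan says.** **Text.** SAP Endpoints defines the primary endpoints as percent change in aBMD "in the non-dominant (1) total hip and (2) femoral neck skeletal sites". SAP Primary analyses sets the order: "Multiplicity will be handled by utilizing a fixed-sequence approach to testing, with initial analysis of total hip" at 0.05, then femoral neck at 0.05 if total hip succeeds. The key secondary endpoints are integral bone mineral content by QCT at three sites. Distal femoral epiphysis is the first, and the list continues "2) Int. vBMC tibial epiphysis, and (3) Int.vBMC distal femoral metaphysis measured by QCT". SAP Secondary analyses, part (b), states: "The primary analysis described above will be applied for all the three key secondary endpoints at 6, and 12 months visits". Part (c) extends the primary and secondary endpoints to 24 months, with baseline hip aBMD as the baseline covariate.

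**Table.** The first row of the Analysis Plan Summary agrees with the text: total hip and femoral neck are primary, with a total hip/femoral neck baseline. The fourth row then reads "Change from Baseline at 6, 12 months with femoral neck aBMD, DXA (b"). It is labelled a secondary analysis and has baseline total hip aBMD as covariate. The footnote defines (b) as the secondary endpoints at 12 months. The other (b) rows are femoral epiphysis and femoral metaphysis. The (c) rows are total hip, femoral neck, femoral epiphysis and femoral metaphysis. No row mentions the tibia.

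**The concern.** The table is where the SAP assigns each endpoint a role, a covariate set and a missing-data method, so a programmer is likely to work from it. Followed literally, it has three effects.

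- Femoral neck is analysed twice at the same visits. The second analysis has a different covariate and no stated gate on total hip, so a femoral neck result could be reported even if the total hip test failed.
- Tibial epiphysis drops out of the key secondary family and femoral neck is in it. In a stepwise adjustment, an endpoint's adjusted p-value depends on which other endpoints are in the family. If the order is the numbering in Endpoints, tibial epiphysis also stands ahead of femoral metaphysis, so removing it changes what metaphysis has to pass.
- Femoral neck (outside the primary row) and the QCT endpoints are adjusted for total hip aBMD at baseline, not for their own baseline values.

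Nothing in the SAP says whether text or table prevails, so the choice is left until results can be seen.

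**Working it through.** **1. The plan's own figure.** Protocol 14.3 gives 80% power with 30 per group for d = 0.74, and for a 6.5% difference with SD 9.02%. Assume a two-sided test at 0.05 and power = Φ(d·√(n/2) − 1.96), with √(30/2) = 3.873.

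- d = 0.74: 0.74 × 3.873 − 1.96 = 0.906, power 81.8%.
- d = 6.5/9.02 = 0.7206: 0.7206 × 3.873 − 1.96 = 0.831, power 79.7%.

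The two-sample t versions are 80.5% and 78.4%. The stated 80% reproduces, and nothing below changes it.

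**2. Analyses required by the text against rows in the table.** Sensitivity and WISCI-interaction analyses are left out.

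| Endpoint | Text, 6/12 mo | Table, 6/12 mo | Text, 24 mo | Table, 24 mo |
|---|---|---|---|---|
| Total hip aBMD | 1 primary | 1 primary | 1 | 1 |
| Femoral neck aBMD | 1 primary | 1 primary + 1 secondary | 1 | 1 |
| Distal femoral epiphysis | 1 secondary | 1 secondary | 1 | 1 |
| Tibial epiphysis | 1 secondary | 0 | 1 | 0 |
| Distal femoral metaphysis | 1 secondary | 1 secondary | 1 | 1 |

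The mismatches are one extra femoral neck row and two missing tibial entries. The rows left out show a related gap. The sensitivity and interaction rows name total hip only, while the text repeats the primary model for the first and names both hip sites for the second.

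**3. The secondary family at 6/12 months.**

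- Text: femoral epiphysis, tibial epiphysis, femoral metaphysis.
- Table (b): femoral neck, femoral epiphysis, femoral metaphysis.

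Each has three members and two are shared. The number of tests is the same, but the set on which the adjusted p-values are computed is not.

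**4. Baseline covariates.** Of the table's ten rows, the first carries the total hip/femoral neck baseline and the other nine carry baseline total hip aBMD (written BMD in the last). Three of the nine have total hip as outcome: sensitivity, interaction and 24-month. That leaves 9 − 3 = 6 rows with another site's baseline: two for femoral neck (6/12 and 24 months) and four for QCT. Part (b) of the text names no separate baseline for the QCT endpoints, and part (c) names the hip. The text therefore does not settle the covariate for these endpoints.

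**5. Size of the femoral neck duplication, if both tests could be claimed.** Two independent tests at 0.05 give 1 − 0.95² = 9.75%. The two models share an outcome, so the true figure is lower. A null simulation used 40,000 trials per setting and one outcome, with two ANCOVAs differing only in the baseline covariate. It assumed:

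- 30 or 24 per arm (24 = 30 × 0.8, the protocol's 20% drop-out figure);
- baseline-to-baseline correlation 0.6 to 0.9;
- own-baseline-to-change correlation 0 to 0.7.

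Each test alone rejected in 4.8% to 5.3% of trials. At least one rejected in 5.3% (30 per arm, correlations 0.9 and 0) to 8.0% (24 per arm, 0.6 and 0.7). The correlations are not in the documents. The simulation has one visit, so it is simpler than the SAP's mixed model, and it ignores the gate on total hip.

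**The case against.** The best defence is that the table is only a summary and the text is clear. Endpoints, Primary analyses and the table's first row all give femoral neck one role: primary, second in sequence. Femoral neck is not among the key secondary endpoints, so the (b) row contradicts its own footnote and reads as a drafting slip. The table is also not exhaustive, since additional secondary and exploratory endpoints have no rows.

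Much of this stands, and it rules out four stronger readings.

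- *That tibial epiphysis will go untested.* The text commits to all three key secondary endpoints at 6 and 12 months and to the secondary endpoints at 24 months. Only the table omits it.
- *That the femoral neck row was put in place of the tibial row.* The count of three (b) rows fits this, but the documents do not say so. At 24 months femoral neck belongs in the table and the tibial row is still missing, so substitution does not explain both gaps.
- *That the analyst may pick either femoral neck p-value at 0.05.* No passage permits this, so 5.3% to 8.0% shows what could happen and is not a property of the plan.
- *That the total hip covariate is peculiar to the femoral neck (b) row.* It runs through every secondary row. Nor does it bias the randomised comparison, since each model alone held close to 5% in the simulation. The price is likely lower precision and an analysis not matched to its endpoint.

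The defence does not remove the conflict. The SAP has no rule that text overrides table, and for the QCT endpoints at 6/12 months the table is the only place that specifies a baseline.

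**Conclusion.** The concern holds as a conflict between the SAP's summary table and its text. It has three parts: femoral neck at 6/12 months is both primary and a secondary (b) row, the latter with the total hip baseline and no stated gate; tibial epiphysis, a key secondary endpoint, has no row at 6/12 or 24 months, so table and text define different secondary families; and six of ten rows use another site's baseline.

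This is more than clerical, because the table sets roles, covariates and the tested family. It is still moderate. The text supports one sensible reading of the roles and the family, and sample size and power do not change. The row counts need no assumptions beyond the table as printed. A row lost in PDF conversion is unlikely, as the tibia is absent from both time blocks. The type I error range rests on the assumed correlations.

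A reader might also infer from the protocol, where the primary endpoint is "Mean change in BMD from baseline after one year, evaluated by DXA at the total hip", that this point calls for demoting femoral neck. It does not. One primary site in the protocol against two in the SAP is a separate difference to reconcile, and settling it would not repair the table.

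**What to change.** 1. Delete the femoral neck (b) row, or label it non-confirmatory. Keep femoral neck only as step 2 of the fixed sequence, adjusted for baseline femoral neck aBMD.
2. Add tibial epiphysis rows at 6/12 months and at 24 months.
3. Use each endpoint's own baseline as covariate in every secondary row, and make the same change to the 24-month model in Secondary analyses (c).
4. State that the key secondary family is the three QCT endpoints listed in Endpoints.

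While editing, check the sensitivity and interaction rows, which name total hip only, against the text.

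The cost is edits to the SAP table and to a sentence in Secondary analyses, with no new data, visits or participants. The documents do not say whether treatment codes have been broken. The change is worth most if it is dated before that.
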